## 5.2. Rationale

Osteoarthritis (OA) is a disease of the synovial joints characterized by the loss of cartilage, subchondral sclerosis, cyst formation, joint deterioration and new bone (osteophytes) formation around the joint. In addition, the properties of synovial fluid, to act as a shock absorber and lubricant for the joint surfaces, are impaired (Balazs, et al., 1993). In the shoulder joint, osteoarthritis is a common disorder that leads to pain, progressive loss of function and diminished quality of life. Glenohumeral osteoarthritis usually presents as gradual pain and loss of motion in patients older than 50 years (Self, 2002; Iannotti, et al., 2005; Stevenson, et al., 2002). A history of arthritis, previous shoulder surgery, pain, crepitus, and decreased motion is consistent with the diagnosis.

Currently, no curative therapy is available for osteoarthritis, and thus the overall goals of management are to reduce pain and prevent disability. Traditional treatments for OA include simple analgesics, NSAIDs, IA corticosteroid injections, physiotherapy, activity modification, weight reduction, orthotics, and surgery (Hochberg, et al., 2012). NSAIDs have proven therapeutic efficacy, but have been noted to have important adverse effects such as gastrointestinal bleeding, liver or kidney toxicity, and cardiac disorders. In addition the economic burden of providing medical treatment for adverse events (AEs) of NSAIDs has been estimated to be more than US \$4 billion a year. Intra-articular corticosteroid injections, although useful for moderate to severe OA not responsive to conservative treatments, is contraindicated in diabetics and osteoporotic patients or those at risk. Normally, all other treatment options should be fully exploited prior to surgical management of OA, which is expensive, painful, and not risk-free. Taking into consideration that chronic use of some oral pain medications may be contraindicated, a locally-delivered therapy with no known drug interactions and an excellent safety profile is a valuable treatment option for patients.

Hyaluronic acid is an important component of synovial fluid and cartilage matrix and contributes to the homeostasis of the joint environment. Various clinical trials in the recent years have shown that hyaluronic acid replacement showed significant improvement compared with baseline (Colen, et al., 2012). The OARSI (Osteoarthritis

Research Society International) has concluded that intra-articular injection of hyaluronic acid may be useful in patients with knee or hip OA. Hyaluronic acid can be used in patients with contraindications to NSAIDs and corticosteroids or in patients not suitable for operative treatment. Hyaluronic acid (HA) is a polysaccharide secreted into the normal joint space by type B synoviocytes or fibroblasts, and it has viscoelastic properties for lubrication and chondroprotective effects. Recent studies of human synoviocytes from osteoarthritic joints have revealed that exogenous hyaluronic acid stimulates de novo synthesis of hyaluronic acid (Smith, et al., 1987), inhibits release of arachidonic acid, and inhibits interleukin-1 $\alpha$ -induced prostaglandin E2 synthesis by human synoviocytes, which reduces the anti-inflammatory response (Yasui, et al., 1992). Hence, replenishing the hyaluronic acid component of normal synovial fluid may play a role in supplementing the elastic and viscous properties of synovial fluid (Balazs, 1993; Balazs, 1982), which may help relieve signs and symptoms related to OA and improve shoulder function.

Recently a large (660 subjects) randomized, double-blind, multicenter trial was conducted in the United States to compare the HA product Hyalgan® (HA) (Sanofi-Aventis) to saline injections over a 6-month period for the treatment of chronic shoulder pain. Based on radiographic criteria, subjects were stratified at baseline into two major groups: those with GH osteoarthritis (GH-OA) (60%) and those without GH-OA (40%). Using MRI and other clinical criteria, subjects were further sub-categorized by presence of adhesive capsulitis and rotator cuff pathology at baseline. The subjects were randomized into one of three treatment groups: five injections of saline, five injections of HA, or three injections of HA and two injections of saline. The intent to treat (ITT) longitudinal analysis revealed the five HA injection group and the three HA plus two saline injection group improved significantly more than the group receiving five saline injections over the 6-month period. There were no significant differences between the groups receiving three or five HA injections. Although all groups demonstrated improvements from baseline, the greatest treatment benefit was seen in the group of patients with GH-OA. In addition, statistically significant improvement in pain was observed in the OA group, regardless of the presence of other shoulder pathologies including rotator cuff tears or adhesive capsulitis. The improvement in pain in the non-OA group was not statistically different from the saline control group. These findings suggest HA's therapeutic effect on the shoulder was related to the presence of OA and not to other pathologies such as rotator cuff tears. The safety profile was favorable, with a low incidence of injection site pain (<1%) and no significant differences in pain between the HA and saline groups.

HA product injections exert their therapeutic effects on pain by a non-pharmacologic mechanism, are not associated with any catabolic actions on the joint tissue, and have been repeatedly administered over several years in both the knee and hip. DUROLANE has been proven to be an effective treatment for OA in the knee with a low percentage of adverse events (AEs). Because DUROLANE has demonstrated a successful history of pain relief in the knee with a very low rate of AEs, we believe it will demonstrate similar effectiveness for pain relief in the shoulder.

The purpose of this study is to assess whether the use of a HA-containing synovial fluid substitute (DUROLANE®) will relieve pain and result in an improvement of joint function

in patients presenting with persistent shoulder pain due to OA. It also seeks to evaluate its safety and tolerability. Clinical trials with DUROLANE and other HAs have shown a sustained response to treatment up to 26 weeks at least (Agerup, et al., 2005; Edsman, et al., 2009). Using this as a basis, the effectiveness and safety assessments for this study will be collected over 26 weeks.

In conclusion, the results of this study should support the current indications in the EU, specifically, for symptomatic treatment associated with mild to moderate osteoarthritis pain in the shoulder joint.

### **5.3. Potential Risks and Benefits**

#### **5.3.1. Potential Risks**

##### **5.3.1.1. Risks Associated with the Use of DUROLANE**

There is a lack of published data related to the use of viscosupplementation for joints other than the hip and knee (e.g. ankle, shoulder, temporal mandibular joint, etc.). The majority of the reported adverse reactions in DUROLANE clinical studies of the knee and hip were described as transient pain, swelling and/or stiffness locally in the joint. It is unclear if these adverse reactions were related to the injection procedure or DUROLANE. These adverse reactions were mild or moderate in intensity and only occasionally required treatment with analgesics. A review of the literature related to the use of other HA preparations in other joints did not reveal any additional unique AEs (Durolane IFU, 2012). The type of adverse reactions associated with the use of DUROLANE in shoulder are likely to be the same as those observed in hip and knee.

The differences in physical and chemical properties between DUROLANE and other HA preparations have been assessed not to influence the safety and tolerability when injected intra-articularly (Q-Med, 2012). The risks associated with the IA injection will be minimized by only allowing clinicians to participate who have adequate education and are experienced in the delivery of IA shoulder therapies.

As with any treatment, unexpected reactions may occur. The study contains an exclusion criterion for those subjects with a previous history of an allergic response to a HA-based product. However, should a reaction occur, the subjects will be informed to contact the study site immediately and be given immediate advice about any necessary medical treatment.

Many subjects with shoulder pain receive treatment with anti-inflammatory drugs. Subjects who decide to take part and are receiving anti-inflammatory drugs must stop such treatment for a time sufficient for the given medication to clear the body (at least 5 half-lives of drug activity) before the shoulder injection is made and refrain from using such medications during the rest of the study period. This may increase the risk that study subjects experience shoulder or other bodily pain. However, to mitigate such risk, all subjects will be allowed to take rescue medication (acetaminophen) during the study for such pain. Other analgesics are prohibited.

All subject use of rescue medication will be recorded in the CRF.

### **5.3.1.2. Risks Associated with Injection**

Certain risks are specifically associated with insertion of a needle into the IA joint space, irrespective of the device. Such risks include bleeding, infection, and joint injury, all of which are rare.

The risks associated with IA injections can be minimized by choosing appropriate technique, and ensuring accurate needle placement into the IA joint space. Image guidance of the needle (via ultrasound or fluoroscopy) is allowed but not required in this study. Additionally, strict aseptic procedures should be maintained during the procedure to reduce the risk of infection.

### **5.3.2. Known Potential Benefits**

Taking part in this study may improve the subject's shoulder OA pain.

Information from this study may help Investigators learn more about symptomatic shoulder OA, treatment for persistent shoulder pain or help identify who is more likely to benefit from DUROLANE treatment.

This information may help future patients with shoulder OA pain.

## **6. TRIAL OBJECTIVES AND PURPOSE**

### **6.1. Study Objectives**

#### **6.1.1. Primary Objective**

To evaluate the efficacy of a single intra-articular (IA) injection of DUROLANE 3mL given for the relief of pain in the treatment of symptomatic osteoarthritis (OA) of the shoulder followed over a 26-week time period.

#### **6.1.2. Secondary Objectives**

To evaluate the efficacy of a single IA injection of DUROLANE 3mL given for treatment of symptomatic OA of the shoulder followed over a 26-week time period for:

- shoulder pain at night
- shoulder range of motion
- shoulder pain rescue medication use

To evaluate the safety and tolerability of a single IA injection of DUROLANE 3mL over a 26-week time period

### **6.2. Study Outcome Measures**

#### **6.2.1. Primary Outcome Measures**

The primary outcome measure is the Shoulder Pain on Movement (SPOM) VAS (0-100mm) scale.

#### **6.2.2. Secondary Outcome Measures**

Secondary outcome measures will include the Shoulder pain at night (SPAN) VAS (0-100mm) scale, American Shoulder and Elbow Surgeons (ASES) Standardized Shoulder Assessment (which includes range of motion and patient self-evaluation of pain today and activities of daily living), Patient Global Assessment (PGA) VAS (0-100mm) scale and Shoulder pain rescue medication diary.

Safety and tolerability of DUROLANE 3mL will be assessed through the collection of concomitant medications, SAEs and AEs related to the injection procedure and the device. Physical exams will be performed as needed. Consumption of rescue medication will be collected via subject diaries.

## **7. INVESTIGATIONAL PLAN**

### **7.1. Overall Study Design**

This is a prospective, open-label, single-cohort study to evaluate pain and function outcomes and safety following a single IA injection of DUROLANE 3mL in subjects with symptomatic shoulder OA. The study will be performed at one site in Canada with potential to add additional sites to boost recruitment, if required.

Adult subjects who have been clinically diagnosed with symptomatic mild to moderate OA of the shoulder that meet the inclusion and exclusion criteria will be recruited after providing written informed consent. Patients reporting pain per the SPOM VAS (0-100mm) scale  $\geq 50$ mm and radiographic evidence of OA will be screened for eligibility. Subjects should be willing to discontinue use of oral analgesia, other than acetaminophen use. Subjects with significant pain from other joints (neck, hand, hip, knee, ankle), or report of  $>20$ mm on SPOM VAS (0-100mm) scale for the contralateral shoulder, will not be eligible to enroll in the study.

The study will consist of a screening visit, a Baseline Visit (Week 0) during which an IA shoulder injection will be given and follow-up clinic visits at Week 6, Week 12, and Week 26 after the Baseline Visit. There will be a telephone contact at Week 18 to collect efficacy assessments (excluding the physician range of motion assessment), adverse events, concomitant and rescue medication use.

The effectiveness assessments (excluding range of motion) are completed by the patient and the same evaluating investigator should preferably see the patient at all visits including the eligibility check at the screening visit.

### **7.2. Number of Subjects**

In total, approximately 39 subjects will be screened and 36 subjects will be enrolled for up to 29 evaluable subjects.

### **7.3. Treatment Assignment**

This is an open-label, single-treatment study. Qualified subjects will be assigned to DUROLANE 3mL only.

### **7.4. Study Schedule**

Written informed consent will be obtained from prospective subjects prior to enrollment to the study. The assessments to be done at each visit are shown in [Table 2](#). In case of any withdrawal (subject drop-out before the completion of the intended follow-up period), the date and reason for withdrawal will be collected in the CRF.

**Table 2: Schedule of Events**

Activities	Visit 1 (screening)	Visit 2 (baseline)	Visit 3	Visit 4	Visit 5 (telephone contact)	Visit 6 (final study visit)
	Week -1 to -2 (≤ 14 days)	Week 0 (Day 0)	Week 6 (±7 days)	Week 12 (±7 days)	Week 18 (±7 days)	Week 26 (±7 days)
Informed consent	X					
Review of inclusion/exclusion criteria	X	X				
Demographics	X					
Medical history, including shoulder OA	X					
X-ray of the study shoulder	X 					
Review of concomitant medications/therapies	X	X	X	X	X	X
Physical examination including height and weight, vital signs	X	X	2	2		X
Physical examination of the study shoulder (SS)	X	X	X	X		X
Physical examination of the contralateral shoulder	X	X				
Washout of analgesics	X 	X 	X 	X 	X 	X 
Urine pregnancy test		X 				
VAS Shoulder pain on movement – contralateral shoulder	X	X				
VAS Shoulder pain on movement – SS	X	X	X	X	X 	X
VAS Shoulder pain at night – SS		X	X	X	X 	X
VAS Patient global assessment		X	X	X	X 	X
ASES Patient self-evaluation (VAS pain today and ADL only) – SS		X	X	X	X 	X
ASES Physician assessment range of motion only – SS		X	X	X		X
Dispense Week 18 VAS pain, PGA, and ASES patient self-evaluation forms				X		
Intra-articular shoulder injection		X				
Instruct subject on rescue medication use	X	X	X	X	X	
Dispense shoulder pain rescue medication diary	X					
Review shoulder pain rescue medication diary and record intake on CRF		X	X	X	X	X
Review and report adverse events (AEs)		X	X	X	X	X
Collect shoulder pain rescue medication diary						X

1. If a radiograph was not taken within 6 months of the screening visit, then a radiograph must be taken as standing x-rays in the anterior-posterior and lateral plane views. Radiographs must be read by a local radiologist or the orthopaedic surgeon.
2. As clinically indicated.
3. At least 5 half-lives of current analgesic must have passed before Baseline Visit to confirm eligibility.
4. No acetaminophen is to be taken for 24 hours before each study visit (Weeks 0, 6, 12, 18, 26). No other analgesic is to be taken during the course of the study.
5. Urine pregnancy test will be performed on all females of childbearing potential.  
At the Week 12 visit VAS pain, PGA, and ASES patient self-evaluation forms will be dispensed to the subject to be completed at the time of the Week 18 telephone contact.

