The subject will receive, as part of the informed consent, a written explanation of shoulder OA and the anticipated AEs associated with DUROLANE injection. Subjects should also be informed about medications which are permitted and medications which are prohibited during the study period (see [Appendix 2](#)). In addition, subjects should be informed about post-injection procedures (see Section [9.4.6](#)).

Acetaminophen will be purchased by the research subject as needed. The research site staff will provide written instructions that the dose should not exceed 4g/day and no analgesics are to be taken 24 hours prior to any study visit. No other analgesic medication is permitted during study participation. A shoulder pain rescue medication diary will be provided to record intake of rescue medication and other concomitant medications used throughout study participation. The shoulder pain rescue medication diary will have written instructions on how to record use of rescue and concomitant medications. In addition, instructions on rescue medication dosing and wash-out periods prior to study visits will also be provided.

Screen failures will be recorded in the Screening Log, including a clear description for screen failure rationale. For subjects determined to be eligible, the date of enrollment will be entered into the Enrollment Log.

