Subjects will be informed about possible anticipated AEs following the IA injection. The shoulder pain rescue medication diary will be reviewed and any necessary counseling regarding use of rescue and other concomitant medication will be given as needed. The shoulder pain rescue medication diary will be returned to the subject at each visit starting from the Screening Visit to record intake of rescue medication and other concomitant medications.

Instructions on how to take acetaminophen as rescue medication will be provided. The subject will again be reminded that the acetaminophen intake should not exceed 4g/day and that none is to be taken 24 hours prior to any study visit. Subjects will also again be reminded that no other analgesia should be used during study participation.

If for any reason, injection is not possible during the Baseline Visit (Week 0), the injection may be rescheduled for up to two days after the Baseline Visit provided it is within 14 days from the Screening Visit. Subsequent study visits will be based on calendar days from the date of the Day 0 injection. Eligibility must be reconfirmed prior to injection.

Thereafter, at Investigator's discretion, topical anesthesia (using ethyl chloride or lidocaine spray) or subcutaneous lidocaine may be given followed by the IA injection of DUROLANE. If effusion is found in the shoulder upon needle placement in the joint

space, it must be removed (arthrocentesis) before DUROLANE is injected. The amount of fluid removed will be documented in the CRF. The injection procedure will be conducted by the Investigator. See Section 9.4 for more details.

Image-guidance may be used to ensure proper IA placement of the treatment with the assumption that the investigator is experienced with the use of the type of imaging used.

To monitor for possible injection procedure-related events, subjects should remain at the study site for 30 minutes following injection. Acetaminophen to relieve post-injection pain is allowed. All subjects should be informed about post-injection procedures (see Section 9.4.6).

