#### **7.4.3. Follow-up Visits (Weeks 6, 12 and 18)**

Weeks 6 and 12: Subjects will return to the clinic for Visit 3 (Week 6) and Visit 4 (Week 12) after the baseline injection of DUROLANE. The SPOM VAS (0-100mm), SPAN VAS (0-100mm), ASES patient self-evaluation (VAS pain today and activities of daily living only), and ASES physician ROM assessment will be completed for the study shoulder only. The PGA (0-100mm) will also be completed at this visit. If clinically indicated, a full physical examination will be performed.

Week 18: Patients will receive a follow-up telephone call from the research staff at Visit 5 (Week 18) after the baseline injection of DUROLANE. The subject will be asked to complete the SPOM VAS (0-100mm), SPAN VAS (0-100mm), and ASES patient self-evaluation (VAS pain today and activities of daily living only) for the study shoulder. The PGA (0-100mm) will also be completed at this visit. All efficacy assessments will be returned to the study site by mail.

At all visits: Subjects will be queried about any AEs since the last visit. The subject diary for rescue and other concomitant medications will be reviewed and any necessary counseling regarding use of rescue and other concomitant medication will be given as needed. Use of rescue medication and concomitant medication since last visit will be recorded on the CRF. Instructions that the acetaminophen dose should not exceed 4g/day and that the 24-hour wash-out prior to any study visit will be discussed with each subject at length. The subject shall also be reminded that no other analgesia should be used.

Return the shoulder pain rescue medication diary to subjects at each clinic visit (excluding Week 18), unless a replacement is needed. This enables the subject to record their intake of rescue medication and other concomitant medications used between clinic visits.

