#### **9.4.6. Post-Injection Care**

To monitor for possible injection procedure-related events, subjects should remain at the study site for 30 minutes following injection.

The subjects should be encouraged to rest the injected joint as much as possible for at least 24 hours. Subjects are allowed to return to work, but strenuous activities and driving long distances should be avoided the first 48 hours after injection.

Subjects should be informed that there could be pain associated with the injection procedure. For post-injection pain management, subjects should rest and apply ice at the injection site for 20-minute intervals, if needed. In the event of persistent pain, the subject may take recommended rescue medication (see Section 10). All pharmacological and non-pharmacological treatments of post-injection pain must be captured in the CRF.

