#### **9.4.8. Reporting Technical Complaints**

All technical complaints regarding the Investigational Product are to be reported to the Sponsor promptly.

AEs and other clinical findings prior, during or immediately post-injection must be recorded. Subjects experiencing pain and swelling at the study shoulder or any other AEs will be instructed to contact the study staff.

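### No adverse-event query or symptom record is scheduled between the injection visit and Week 6, so mild local reactions that subjects neither report nor treat may be under-recorded

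*Protocol*

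**What the plan says.** **Objective.** Section 6.1.2 makes safety and tolerability of the single injection over 26 weeks a secondary objective.

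**Expected reactions.** Section 5.3.1.1 describes most reactions in the sponsor's knee and hip studies as "transient pain, swelling and/or stiffness locally in the joint". It says that they were mild or moderate, seldom needed analgesics, and are likely to be of the same type in the shoulder.

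**Scheduled capture.** On the day of injection, "subjects should remain at the study site for 30 minutes following injection" (Section 9.4.6). Table 2 marks the row "Review and report adverse events (AEs" at Weeks 0, 6, 12, 18 and 26, with a ±7-day window after Week 0. At the follow-up contacts, "Subjects will be queried about any AEs since the last visit" (Section 7.4.3).

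**Diary.** Section 7.4.1 gives its purpose: "A shoulder pain rescue medication diary will be provided to record intake of rescue medication and other concomitant medications used throughout study participation". Sections 7.4.2, 7.4.3 and 10 describe it in the same terms. No symptom field is mentioned.

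**Subject-initiated capture.** Section 9.4.8 states: "Subjects experiencing pain and swelling at the study shoulder or any other AEs will be instructed to contact the study staff". Section 5.3.1.1 asks for immediate contact if a reaction occurs, Section 7.4.6 allows unscheduled visits at the subject's request, and Section 9.4.6 requires drug and non-drug treatment of post-injection pain to be entered in the CRF.

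**The concern.** The reactions that the protocol most expects are short and local, and they would arise in the first days after injection. That stretch falls inside the gap between the injection visit and the first follow-up query, and nothing in the subject's hands is described as recording symptoms during it.

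Three features make recovery at Week 6 difficult:

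- Subjects enter with pain on movement of at least 50 mm and have stopped other analgesics, so a brief flare is hard to tell from background pain weeks later.
- Section 14.1.2 requires the investigator to categorise each event by severity and likelihood of causation, which is easier with a known onset and duration.
- The study has a single arm, so incomplete capture is not offset by an equally affected control group.

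At stake is how completely early local tolerability is described: how often reactions occur, when they start and how long they last. Section 5.3.1.1 admits that it is unclear whether earlier reactions came from the procedure or the product, and Section 5.1.2 remarks that one shoulder publication did not report time to resolution. The present schedule risks leaving the same questions open.

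**Working it through.** **1. Length of the gap.** Section 7.4.2 fixes the clock: "Subsequent study visits will be based on calendar days from the date of the Day 0 injection". Week 6 is 6 × 7 = 42 days. With the ±7-day window in Table 2, the first scheduled query falls between 42 − 7 = 35 and 42 + 7 = 49 days after injection, or 5.0 to 7.0 weeks. Table 2 has no contact of any kind between.

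**2. What each source could show for a mild reaction in the first days.**

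| Source | What it captures | Limit |
|---|---|---|
| On-site observation (9.4.6) | Events in the first 30 minutes | Ends before the subject leaves |
| Contact with staff (9.4.8, 5.3.1.1); unscheduled visit (7.4.6) | Whatever the subject chooses to report | Section 9.4.6 tells subjects that injection pain may occur and to rest and use ice, so a call about a mild reaction is less likely |
| Medication diary (7.4.1, 10) | Dated acetaminophen intake | Reactions seldom needed analgesics (5.3.1.1); the drug is also rescue for osteoarthritis pain (12.5) and preferred for other body pain (10), so an entry does not identify a reaction |
| CRF record of post-injection pain treatment (9.4.6) | Drug and non-drug treatment | Untreated reactions leave no trace; no diary field for ice or rest is described |
| Pain on movement and at night scales (12.1, 12.2) | Pain over the last 24 hours | First repeated at Week 6 |
| Week 6 query (Table 2, 7.4.3) | Events since the last visit | Recall over 35 to 49 days |

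The one class of event for which only the last row remains is the mild, transient reaction that the subject neither reports nor treats.

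**3. Size.** The protocol gives no local-reaction rate for this product in the shoulder and no figure for how complete reporting is, so the loss cannot be calculated. As an illustration only, take 36 treated subjects (the planned minimum enrolment), an assumed true reaction rate p and an assumed captured share s:

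expected subjects reported = 36 × p × s; observed rate = p × s

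| p (assumed) | s = 100% | s = 75% | s = 50% |
|---|---|---|---|
| 10% | 3.6 (10%) | 2.7 (7.5%) | 1.8 (5%) |
| 30% | 10.8 (30%) | 8.1 (22.5%) | 5.4 (15%) |

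Each subject whose reaction is missed lowers the observed incidence by 1/36 = 2.8 percentage points. These figures show scale and are not evidence that anyone would be missed.

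**The case against.** The strongest reply is that the protocol contains no error here. It uses open questioning at visits plus spontaneous reporting, which is a recognised approach, and it supports it: subjects are told about anticipated events at screening and again at baseline, asked to contact the site, offered unscheduled visits, and have post-injection treatment recorded. The text of Appendices 3 and 4 and the diary form itself are not in the copy reviewed. A symptom diary also has a cost, because subjects with established shoulder pain would record their osteoarthritis and no control arm would separate it.

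Much of this stands. It rules out three stronger readings that a reader might infer:

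- *That early reactions as a class depend on recall.* They do not; reported or treated reactions have an earlier route into the record.
- *That tolerability will look better than it is.* The direction is likely, but the protocol does not show that under-recording will occur or how large it would be.
- *That one or two missed cases would change the safety conclusion.* Section 14.1 plans no safety test and sets no threshold. The injection-site pain rates of 1.4% to 3.2% in Section 5.1.2 would give 36 × 0.014 = 0.5 to 36 × 0.032 = 1.2 subjects, but they come from three- or five-injection regimens of another product, and the lower figure is also that trial's saline rate. They are not an expectation for this injection.

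What the reply does not remove is the residual gap. Every early route it names after the subject leaves the site starts with the subject's decision to call, to attend or to take treatment.

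**Conclusion.** The point holds as a limited weakness in data capture. After 30 minutes on site, no adverse-event query is scheduled for 35 to 49 days, and the only record described as being in the subject's hands is for medication. Mild, transient local reactions that are neither reported nor treated therefore depend on 5 to 7 weeks of recall. Their incidence, onset and duration may be under-recorded, in the device's favour.

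The size is unknown, and safety results are descriptive, so the consequence is a less complete account of early tolerability and not a wrong decision. The conclusion assumes that the diary form holds no symptom field beyond what the protocol describes, and that the appendices not shown add no early scheduled contact. This is a worthwhile small improvement, not a defect that threatens the study.

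**What to change.** Add one dated page to the diary that subjects already hold, covering a short fixed period after injection. Fourteen days is offered as an example; the protocol supplies no basis for a particular length. For the study shoulder it should ask about pain, swelling and stiffness that is **new or worse than before the injection**, with intensity and first and last day. The comparison with the pre-injection state matters, because a plain present-or-absent line would mostly record existing osteoarthritis pain. Review the page at Week 6 under the diary-review row already in Table 2, and amend the diary description in Section 7.4.1 to match.

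The cost is one diary page and one CRF page, with no added visit or call. The downsides are more mild events to code, and some entries reflecting background symptoms that the investigator must attribute without a control arm. The page would still be reviewed only at Week 6, so it improves the dating and completeness of the record, not the speed of reporting; the existing instruction to contact staff stays in place for that.
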